## **12.2 Clinical Laboratory Assessments**

The laboratory parameters below will be summarized at baseline and at each post-baseline time point by treatment group, using the SAS. CFBL to each time point including end of treatment for each of the following laboratory parameters will also be summarized by treatment group.

Chemistry: alanine aminotransferase (ALT), albumin, alkaline phosphatase (ALP), aspartate aminotransferase (AST), bicarbonate, blood urea nitrogen (BUN), calcium, chloride, creatine kinase (CK), creatinine, gamma-glutamyl transferase (GGT), glucose, lactate dehydrogenase (LDH), phosphorus, potassium, sodium, (total) bilirubin, (total) protein, estimated glomerular filtration rate (GFR), cystatin-C

Hematology: hemoglobin, hematocrit, leukocytes, basophils, eosinophils, lymphocytes, monocytes, neutrophils, platelets, red blood cell count, mean corpuscular hemoglobin concentration, mean corpuscular hemoglobin, mean corpuscular volume

Coagulation: prothrombin time, activated partial thromboplastin time, international normalized ratio

Urinalysis: pH, specific gravity, NGAL, creatinine, protein, protein/creatinine ratio, albumin, albumin/creatinine ratio

If, for a given subject at a given visit, the absolute count of neutrophils are not provided but segmented and band neutrophils are, segmented and band neutrophils are summed to determine the absolute count of neutrophils. If only segmented neutrophils are provided, they are used as the absolute count of neutrophils. Similarly, if neutrophils/leukocytes are not provided at a given visit but neutrophils (segmented)/leukocytes are, neutrophils (segmented)/leukocytes are used as neutrophils/leukocytes.

If a laboratory value is lower or higher than the detection limit (eg, <XX.X), the value will not contribute to summary statistics but will be included in the listings.

Out-of-range values will be assessed using shift tables. Laboratory values will be identified as low, normal, or high based on the normal ranges provided by the central laboratory. Shift tables for each parameter will display, for each treatment group, the number of subjects with low, normal, and high values at baseline and end of treatment. Percentages will be based on the number of subjects in each category at baseline.

Potentially clinically significant out-of-range values will also be summarized for safety laboratory parameters. The potentially clinically significant (PCS) values are found in Table 3. The number and percent of subjects meeting the criteria below for single occurrences and consecutive (multiple) occurrences will be summarized by treatment group. Summaries will consider any time post-baseline. The denominator for a given percentage will be the number of subjects who are eligible for each criterion (eg, had a post-baseline assessment or had consecutive post-baseline assessments for the corresponding parameter). Additionally, for subjects with post-baseline chemistry laboratory values meeting the PCS criteria at consecutive visits, all laboratory values (including urinalysis parameters) will be provided in a listing.

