### 9.3.2 Analysis of Safety

Safety will be assessed using the SAS. The assessment of safety will include adverse events, clinical laboratory assessments, ECGs, physical examinations, and vital signs. In addition, the safety assessment will be based primarily on the frequency of new or worsening adverse events, laboratory abnormalities, and serious adverse events (SAEs). Other safety data will be summarized as appropriate.

AEs will be coded using the most recent version of the Medical Dictionary for Regulatory Activities (MedDRA). The summarization of AEs will include only treatment-emergent AEs (TEAEs), defined as AEs that begin or worsen after randomization and ingestion of the first dose of study drug. TEAEs and SAEs will be summarized by system organ class (SOC), severity, and relationship to study drug for each treatment group. Deaths, withdrawal from study treatment due to AEs, and withdrawal from the study due to AEs will each be summarized by treatment group.

Safety laboratory data will be summarized by treatment group at baseline, and at each post-baseline time point, if applicable, and change from baseline to End of Treatment (Week 12) or the ET Visit, if applicable. Baseline for safety laboratory data will be defined as the last pre-dose value (pre-dose Study Day 1/Visit T1 or prior). Frequency counts of new or worsening abnormalities will also be provided.

Vital signs data (value and change from baseline, where appropriate) will be summarized by treatment group at baseline and at each post-baseline time point. Baseline for vital signs data will be defined as the last pre-dose value (pre-dose Study Day 1/Visit T1 or prior). Abnormalities in ECGs and in PEs will be summarized.

All safety data will be listed.

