**Table 3. Lab PCS Criteria**

Laboratory Parameter	Unit	PCS Criteria
ALT	U/L	> 2 × ULN
ALT	U/L	> 3 × ULN
AST	U/L	> 2 × ULN
AST	U/L	> 3 × ULN
BUN	mg/dL	> 2 × ULN
Creatine kinase	U/L	> 3 × ULN
Creatine kinase	U/L	> 5 × ULN
Creatinine	mg/dL	> 0.3 increase from baseline
Estimated GFR	mL/min	Decrease > 15 mL/min from baseline
Hemoglobin	g/dL	Decrease > 1.5 from baseline
Urinalysis Parameter	Unit	PCS Criteria
Protein/creatinine ratio	mg/mmol	> ULN
Albumin/creatinine ratio	mg/mmol	> ULN

ALT = alanine aminotransferase, AST = aspartate aminotransferase, BUN = blood urea nitrogen, GFR = glomerular filtration rate, PCS = potentially clinically significant, ULN = upper limit of normal.

Additionally, urinalysis parameters that are not numeric (ie, blood, bilirubin, glucose, ketones, leukocyte esterase, protein [dipstick results], and nitrite) will be included in a listing. Over the course of the study, there may be lab tests performed that were not specified in the protocol. These tests will not be summarized but will be included in the listings.

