### 12.3 ECGs

ECGs will be performed in triplicate at the Screening Visit, Day 1, Week 2, Week 6, Week 10, Week 12, and the ET Visit, if applicable. The following ECG parameters will be reported by the central reader: heart rate, PR interval, QRS duration, QT interval (uncorrected), QT interval corrected for heart rate using QT interval corrected for heart rate with Bazett's formula (QTcB) and using QT interval corrected for heart rate with Fridericia's formula (QTcF), and T-wave amplitude. The average of the non-missing values for a given ECG parameter (eg, heart rate) will be used for analysis. In cases where only one ECG is performed, the result of the single ECG will be used. CFBL will be calculated for each parameter at each time point (including end of treatment) and summarized by treatment group.

Further, QTcB and QTcF will also be investigated through PCS criteria (see Table 4). The number and percent of subjects meeting the criteria below will be summarized by treatment group using the SAS. Summaries will be given for both overall (ie, any time post-baseline) and by visit. Subjects will be included in all categories for which they qualify. For criteria on the "Actual" values, the denominator for the percentages is the number of subjects who had a post-baseline assessment for each parameter. For criteria on the change, the denominator is the number of subjects who had a baseline and post-baseline assessment.

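### The laboratory PCS counts ignore baseline status although the protocol promises counts of new or worsening abnormalities; this matters mainly for the two urine-ratio rows

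*SAP*

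**What the plan says.** Protocol 9.3.2, in its paragraph on safety laboratory data, states: "Frequency counts of new or worsening abnormalities will also be provided". The synopsis repeats it. For ECGs the same section promises less: "Abnormalities in ECGs and in PEs will be summarized".

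SAP 12.2 tabulates subjects who meet a PCS criterion, once or at consecutive assessments. On timing it says: "Summaries will consider any time post-baseline". The denominator is everyone eligible, meaning subjects who "had a post-baseline assessment or had consecutive post-baseline assessments for the corresponding parameter". Neither numerator nor denominator refers to the subject's baseline status.

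Some criteria in SAP Table 3 are built on change, such as the estimated GFR row ("Decrease > 15 mL/min from baseline"). Others are absolute. The "Albumin/creatinine ratio" row and the protein/creatinine row ask only for a value above ULN.

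SAP 12.2 also plans shift tables of low, normal and high at baseline against end of treatment, with percentages taken within baseline category. For the QTc criteria, SAP 12.3 says: "Summaries will be given for both overall (ie, any time post-baseline) and by visit". SAP 4.3 lists changes from the protocol and does not mention laboratory abnormality counts.

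**The concern.** A subject whose urine ratio is above ULN before the first dose, and stays there, is counted as a post-baseline PCS case. The protocol's wording calls for a count that separates such subjects from those who become abnormal or worsen on treatment. The adverse event tables in SAP 12.1 are restricted in that way through the treatment-emergent definition; the laboratory PCS tables are not.

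Both urine ratios are named safety endpoints (Protocol 2.2.4), and renal function is the laboratory topic given most space in Protocol 1.4. With 30 subjects per arm, a block of pre-existing cases in every arm makes a real difference look smaller. An uneven split of those cases adds noise, because randomisation is stratified only by statin use and qualifying TG.

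**Working it through.** **1. Which Table 3 rows can already be met at entry.** Of 12 rows, 3 are changes from baseline and 9 are absolute.

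| Rows | Type | Entry rule (Protocol 4.2) | Open to pre-existing cases? |
|---|---|---|---|
| Creatinine, eGFR, hemoglobin (3) | Change from baseline | Not relevant | No |
| ALT and AST, > 2 and > 3 × ULN (4) | Absolute | > 2 × ULN excluded at screening | Few |
| CK, > 3 and > 5 × ULN (2) | Absolute | > 3 × ULN excluded at screening | Few |
| BUN > 2 × ULN (1) | Absolute | No limit of its own | Not known |
| Protein/creatinine > ULN (1) | Absolute | Excluded only together with an abnormal urinalysis | Yes |
| Albumin/creatinine > ULN (1) | Absolute | No limit | Yes |

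Type 2 diabetes is allowed, with HbA1c up to 9.5%. The documents do not say how many subjects enter with a raised ratio.

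**2. What the shift tables cover.** Scheduled on-treatment urine ratios are taken at Week 6 and at Week 12 or early termination (Protocol 8.6). A normal-to-high shift at end of treatment is a count of new abnormalities among those at risk. Two cases are left out: a ratio raised at Week 6 that is normal again by end of treatment, and a ratio already high that rises further.

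**3. Size, on assumed rates.** The only planned figure used is the arm size, 30 (SAP 9.1). It reproduces: for a difference of 35, SD 43 and two-sided 5%, 25 evaluable per arm give 80.5% power by the noncentral t (24 give 78.8%), and 25/0.85 = 29.4, rounded up to 30.

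Let b be the share abnormal at baseline, r the chance that such a subject is abnormal again on study, and i the new-onset rate.

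- Planned PCS rate = b·r + (1 − b)·i, over 30 subjects.
- New-onset rate = i, over 30(1 − b) subjects.
- SD of the chance difference between two arms in baseline-abnormal subjects = √(2 × 30 × b(1 − b)).

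Take r = 0.8, with i = 5% on placebo and 25% on drug. For b = 10%, placebo is 0.10 × 0.8 + 0.90 × 0.05 = 12.5% and drug is 0.08 + 0.90 × 0.25 = 30.5%.

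| b | Planned, placebo vs drug | Difference, points | Ratio | New-onset subjects, placebo vs drug | Share of planned placebo count that is pre-existing | SD of imbalance, subjects |
|---|---|---|---|---|---|---|
| 0 | 5.0% vs 25.0% | 20 | 5.0 | 1.5 vs 7.5 of 30 | 0% | 0 |
| 10% | 12.5% vs 30.5% | 18 | 2.4 | 1.4 vs 6.8 of 27 | 64% | 2.3 |
| 20% | 20.0% vs 36.0% | 16 | 1.8 | 1.2 vs 6.0 of 24 | 80% | 3.1 |
| 40% | 35.0% vs 47.0% | 12 | 1.3 | 0.9 vs 4.5 of 18 | 91% | 3.8 |

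At b = 20% the chance imbalance of 3.1 subjects compares with an expected new-onset difference of 6.0 − 1.2 = 4.8 subjects.

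**4. A weaker drug effect.** Take r = 0.9 and i = 5% vs 15%. At b = 20% the planned rates are 0.18 + 0.04 = 22% and 0.18 + 0.12 = 30%. The difference of 8 points has SE √[(0.22 × 0.78 + 0.30 × 0.70)/30] = 11.3 points, or 0.7 SE. Among those at risk the difference is 10 points with SE √[(0.05 × 0.95 + 0.15 × 0.85)/24] = 8.5 points, or 1.2 SE. The same formulas give 0.9 against 1.2 SE at b = 10%, and 0.6 against 1.1 SE at b = 30%.

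**The case against.** The strongest reply is that the protocol does not say the PCS table must carry the new-or-worsening counts, and that the SAP supplies most of them elsewhere. The shift tables use baseline-category denominators, change from baseline is summarised at every time point, and all safety data are listed. With urine ratios scheduled only at Week 6 and Week 12 or early termination, little falls between. The renal changes reported in Protocol 1.4 are in creatinine, BUN and GFR, with no significant change in urine protein, and the creatinine and eGFR rows already refer to baseline. Safety is descriptive, and the rates above are assumed.

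Much of this stands. The gap is narrow, the size is illustrative, and even the new-onset contrast in step 4 is weak. But summaries of mean change and listings are not frequency counts, the shift tables leave out the two cases in step 2, and the departure is undeclared.

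Three stronger readings are tempting, and the documents do not support them.

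- A reader might infer that the QTc tables also break the protocol's promise. That promise sits in the laboratory paragraph and does not extend to ECGs. SAP Table 4 also has increases above 30 and 60 msec for both corrections (4 of its 10 rows). The absolute rows can include cases present at entry: women may enter with QTcF above 450 and up to 470 msec, and QTcB has no entry limit. That affects interpretation but is not a conflict.
- A reader might infer that the ALT, AST and CK rows are new by construction. Those exclusions apply at pre-screening and screening, whereas baseline is the last pre-dose value, normally Day 1. Pre-existing cases should be few, but are not impossible.
- A reader might infer bias between arms. Under randomisation, pre-existing cases are expected equally in each arm.

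**Conclusion.** The point holds for the laboratory PCS counts and has practical weight mainly for the two urine-ratio rows. The SAP does not fully deliver the count the protocol describes, and does not say so. If 10% to 40% of subjects are abnormal at entry, with the persistence and onset rates of step 3, then 64% to 91% of the expected placebo PCS count is entry status, and a fivefold new-onset contrast appears as 2.4-fold to 1.3-fold. The prevalence, persistence and onset rates are assumptions; if few subjects enter with a raised ratio, the effect is small. The consequence is dilution and chance noise in descriptive Phase 2 safety tables. The primary analysis is untouched, so this is a worthwhile improvement and not a serious defect.

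**What to change.** In SAP 12.2, keep the planned PCS counts and add two displays for the absolute laboratory rows, at least the two urine ratios.

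- **New-onset row:** number and percent meeting the criterion post-baseline among subjects who did not meet it at baseline (last pre-dose value, SAP 9.3), with that same group as denominator. Because SAP 12.2 drops values outside the detection limits from summaries, state that a baseline below the detection limit counts as not meeting the criterion.
- **Worst-value shift table:** baseline category against the worst post-baseline value. Split the high category at multiples of ULN fixed before unblinding, so that worsening within it shows. Keeping worsening in this table avoids placing subjects in the new-onset numerator who are not in its denominator.

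If these are not added, SAP 4.3 should declare the departure. A matching new-onset row for the absolute QTc limits in SAP 12.3 is optional.

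The cost is some SAP wording, a few extra table rows, and slightly smaller denominators in the new rows. No new data are needed.

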**Table 3. Lab PCS Criteria**

Laboratory Parameter	Unit	PCS Criteria
ALT	U/L	> 2 × ULN
ALT	U/L	> 3 × ULN
AST	U/L	> 2 × ULN
AST	U/L	> 3 × ULN
BUN	mg/dL	> 2 × ULN
Creatine kinase	U/L	> 3 × ULN
Creatine kinase	U/L	> 5 × ULN
Creatinine	mg/dL	> 0.3 increase from baseline
Estimated GFR	mL/min	Decrease > 15 mL/min from baseline
Hemoglobin	g/dL	Decrease > 1.5 from baseline
Urinalysis Parameter	Unit	PCS Criteria
Protein/creatinine ratio	mg/mmol	> ULN
Albumin/creatinine ratio	mg/mmol	> ULN

ALT = alanine aminotransferase, AST = aspartate aminotransferase, BUN = blood urea nitrogen, GFR = glomerular filtration rate, PCS = potentially clinically significant, ULN = upper limit of normal.

Additionally, urinalysis parameters that are not numeric (ie, blood, bilirubin, glucose, ketones, leukocyte esterase, protein [dipstick results], and nitrite) will be included in a listing. Over the course of the study, there may be lab tests performed that were not specified in the protocol. These tests will not be summarized but will be included in the listings.

### 12.3 ECGs

ECGs will be performed in triplicate at the Screening Visit, Day 1, Week 2, Week 6, Week 10, Week 12, and the ET Visit, if applicable. The following ECG parameters will be reported by the central reader: heart rate, PR interval, QRS duration, QT interval (uncorrected), QT interval corrected for heart rate using QT interval corrected for heart rate with Bazett's formula (QTcB) and using QT interval corrected for heart rate with Fridericia's formula (QTcF), and T-wave amplitude. The average of the non-missing values for a given ECG parameter (eg, heart rate) will be used for analysis. In cases where only one ECG is performed, the result of the single ECG will be used. CFBL will be calculated for each parameter at each time point (including end of treatment) and summarized by treatment group.

Further, QTcB and QTcF will also be investigated through PCS criteria (see Table 4). The number and percent of subjects meeting the criteria below will be summarized by treatment group using the SAS. Summaries will be given for both overall (ie, any time post-baseline) and by visit. Subjects will be included in all categories for which they qualify. For criteria on the "Actual" values, the denominator for the percentages is the number of subjects who had a post-baseline assessment for each parameter. For criteria on the change, the denominator is the number of subjects who had a baseline and post-baseline assessment.

**Table 4. ECG PCS Criteria**

ECG Parameter	Actual or Change	PCS Criteria
QTcB (msec)	Actual	> 450
	Actual	> 480
	Actual	> 500
	CFBL (increase)	> 30
	CFBL (increase)	> 60
	Actual	> 450
QTcF (msec)	Actual	> 480
	Actual	> 500
	CFBL (increase)	> 30
	CFBL (increase)	> 60

CFBL = change from baseline, ECG = electrocardiogram, PCS = potentially clinically significant, QTcB = QT interval corrected for heart rate with Bazett's formula, QTcF = QT interval corrected for heart rate with Fridericia's formula.

All interpretations along with the corresponding details will be provided in a listing.

### 12.4 Vital Signs and Weight

Vital signs comprise pulse rate, diastolic blood pressure (DBP), systolic blood pressure (SBP), respiration rate, and temperature. Except for the Follow-up Visit, vital signs and weight will be measured at all study visits. CFBL and percent CFBL will be calculated for each vital sign and

weight parameter at each time point (including end of treatment) and summarized by treatment group using the SAS.

Vital signs and weight will also be presented in a listing.

## **12.5 Physical Examinations**

A full physical examination will be performed at each subject's first study visit (either at the Pre-Screening Visit or the Screening Visit) and last study visit (either at the Week 12 Visit or the ET Visit). At all other Study Visits (eg, Week 2) where a full physical examination was not conducted except the Follow-up Visit, a symptom-directed physical examination will be performed. Additionally, a symptom-directed physical examination will only be conducted at the Follow-up Visit for subjects who had an abnormal result at Week 12 (or the ET visit) or had an ongoing treatment-related AE.

For each assessment (general appearance, respiratory, etc.), the number and percentage of normal and abnormal findings will be provided by actual treatment group and visit using the SAS. The denominator used to calculate the percentage will be the number of subjects that underwent a physical examination at the corresponding visit.

## **12.6 Plasma Concentrations of Gemcabene**

The concentration of gemcabene will be obtained from reserve plasma samples. Plasma concentration of gemcabene will be summarized using descriptive statistics and presented in a listing.

# **13 OTHER RELEVANT DATA ANALYSES/SUMMARIES**

## **13.1 Medical and Surgical History**

Medical history will be coded using MedDRA version 19.1. Medical history will be summarized by SOC and PT by actual treatment group for the SAS and will be presented in the listings. At each level of summarization, subjects who report one or more medical history events within a given level (SOC/PT) will only be counted once at that level. The table will be sorted by SOC (alphabetically) and then by PT (decreasing frequency in the gemcabene 600 mg column, then the gemcabene 300 mg column within each SOC).

## **13.2 Prior and Concomitant Medications**

Prior and concomitant medications will be coded using the World Health Organization (WHO) Drug Dictionary version 01 Mar 2016. A prior medication is defined as a medication with a stop date prior to the date of the subject's first dose of study drug (ie, medication stop date less than date of first dose of study drug). A concomitant medication is defined as a medication with a start date on or before the date of the subject's last dose of study drug (ie, medication start date less than or equal to date of last dose of study drug) and a stop date on or after the date of the subject's first dose of study drug (ie, medication stop date  $\geq$  date of first dose of study drug);

thus, a medication that is ongoing at the time of the subject's first dose of study drug is considered concomitant. Partial and missing dates will be imputed using rules in [Appendix 2](#).

Prior and concomitant medications will be summarized in separate tables and listings. Medications taken within the period after last dose date and follow-up visit will not be summarized in the tables, but will be included in the concomitant medications listing. Medications will be summarized by ATC level 3 (level 3 indicates the therapeutic/pharmacologic subgroup) alphabetically and preferred name (decreasing frequency in the gemcabene 600mg column, then gemcabene 300 mg column within each ATC) by randomized treatment group for the SAS. At each level of summarization, subjects who report one or more medications within a given level (eg, ATC and preferred name) will only be counted once at that level.

### **13.3 Concomitant Procedures**

A concomitant procedure is defined as a procedure with a start date on or before the date of the subject's last dose (ie, procedure start date less than or equal to date of last dose) and a stop date on or after the date of the subject's first dose (ie, procedure stop date greater than or equal to date of first dose). Concomitant procedures will be presented in a listing containing verbatim terms for the SAS.

## 14 APPENDICES

### Appendix 1. Schedule of Assessments and Procedures

	Pre-Screening a	Screening b,f				Treatment Period c				Follow-Up d	ET
		Study Day -28 to -21	Study Day -14 to -7	Study Day -7	Study Day 1 e	Week 2/ Study Day 15 ± 3 days	Week 6/ Study Day 43 ± 3 days	Week 10/ Study Day 71 ± 3 days	Week 12/ Study Day 85 or up to 3 days prior to Study Day 85		
	Visit Identifier	Visit S1	Visit S2	Visit S3	Visit T1	Visit T2	Visit T3	Visit T4	Visit T5	Study Day 113	Visit FU1
Informed consent	X	X									
Inclusion/exclusion criteria	X	X	X	X	X						
Medical/surgical history and demographics	X	X	X	X	X						
Full physical examination g	X	X							X		X
Symptom-directed physical examination			X h			X	X	X			X i
Vital signs j , height k , and weight	X	X	X	X	X	X	X	X	X		X
Body Mass Index (BMI)	X	X			X			X	X		X
Waist circumference					X				X		X
Urinalysis + NAGL l	X	X			X		X		X		X i
Protein:creatinine ratio; albumin:creatinine ratio	X	X			X		X		X		X i
Serum/urine pregnancy test m	X	X			X	X	X	X	X		X i
Safety chemistry panel, coagulation, and hematology n	X	X	X	X	X	X	X	X	X		X
TSH and serology o	X	X f									
Fasting lipid panel p	X q	X	X	X	X	X	X	X	X		X
Fasting apolipoproteins r					X			X	X		X
LDL-C ultracentrifugation (LDL-C, LDL-TG, VLDL-TG)					X			X	X		X
CI					X				X		X

